13.3.9 Safety Analyses

Routine collection of all AEs and ARs will not take place, due to the well-established safety profile of the study drugs. Rates of constipation and flares of disease activity will be of particular interest. Flares of disease activity will be treated as an AE of special interest and reported on a Flare CRF. Rates of constipation will be collected by participants self-report at week 8 and month 6. Other endpoints related to disease activity (Escalation of Medical

Therapy, Need for Surgery, CRP, and FC) will also be summarised as descriptive statistics and presented by arm

Responsible gastroenterologists will be encouraged to report AEs of special interest and SAEs to the trial team. All AEs, SAEs, and SUSARs will be reported to the DMEC within the relevant time frames, and appropriate action will be taken. Any reported form of self-harm, or suicide will be treated as an IME, whether or not related to taking the trial medication, and reported on an SAE form. Descriptive statistics for all safety data will be summarised by arm.

13.3.10 Adherence

Adherence at 8 weeks and 6 months in the IMP arms is measured by a 4-point-Likert scale.

Adherence will also be assessed via a summary question at 8 weeks and 6 months. For the Amitriptyline arm, the question will be as follows:

""Since you were last asked, which of the options best describes how often you have taken at least one tablet of the trial medication daily?"

- A. Every day or nearly every day
- B. Half of the days or more than half of the days
- C. Less than half of the days
- D. None or nearly none of the days"

For the Ondansetron and Loperamide arms, the summary question at 8 weeks and 6 months will be as follows:

""Since you were last asked, which of the options best describes how often you have taken at least one tablet of the trial medication weekly?"

- A. Every week or nearly every week
- B. Half of the weeks or more than half of the weeks
- C. Less than half of the weeks
- D. None or nearly none of the weeks"

Descriptive statistics, by arm, will be summarised to show the number of adherent patients at each time point, for both of the methods described above.

For those randomised to a low FODMAP diet, adherence at 8 weeks and 6 months will be determined using a 4-point-Likert scale [33]. The question and responses will be as follows:

"Which of the following best describes your adherence to the Low FODMAP diet?"

- A. Continued strict low-FODMAP diet
- B. Reintroduced high-FODMAP foods to tolerance
- C. Continued low-FODMAP diet 50% of the time
- D. Returned to habitual diet

Descriptive statistics will be summarised and presented alongside results of the adherence summary question in the IMP arms, as described above.

FODMAP content will be assessed at 8 weeks and 6 months via the CNAQ [34] in all participants, in order to verify that the FODMAP content is less in the low FODMAP diet arm at follow-up, compared with the other four trial arms. Descriptive statistics only will be presented for the FODMAP content, which will be displayed by arm.

The CNAQ is a semi-quantitative food frequency questionnaire validated to assess FODMAP and nutrient intake, and is determined using an online automated entry system.

14 MONITORING, AUDIT AND INSPECTION

14.1 Monitoring

Trial supervision will be established according to the principles of GCP and in-line with UK Policy Framework for Health and Social Care Research. This will include establishment of a core project team, TMG, an independent TSC, and an independent DMEC. A trial monitoring plan will be developed and will be informed by a trial risk assessment, which will consider the safety or physical or mental integrity of the trial participants and the scientific value of the research. This trial monitoring plan will detail the timing and content of reports to monitor trial conduct, implementation, and adherence with the Consolidated Standards of Reporting Trials (CONSORT). Procedures will be in place to assess risk on an ongoing basis, with adjustments made accordingly.

14.2 Data Monitoring

Data will be monitored for quality and completeness by the CTRU. Missing data will be chased until they are received, confirmed as not available, or the trial is at analysis.

The CTRU/Sponsor will reserve the right to intermittently conduct source data verification exercises on a sample of participants, which will be carried out by staff from the CTRU/Sponsor. Source data verification will involve direct access to patient notes at the participating hospital sites and the ongoing central collection of copies of consent forms and other relevant investigation reports.

14.3 Clinical Governance Issues

To ensure responsibility and accountability for the overall quality of care received by participants during the study period, clinical governance issues pertaining to all aspects of routine management will be brought to the attention of the TSC and, where applicable, to individual NHS Trusts/Health Boards.

15 ETHICAL AND REGULATORY CONSIDERATIONS

The trial will be performed in accordance with the recommendations guiding physicians in biomedical research involving human subjects adopted by the 18th World Medical Assembly, Helsinki, Finland, 1964, amended at the 52nd World Medical Association General Assembly, Edinburgh, Scotland, 1996. Written, informed consent will be obtained from the participants prior to registration into the study. The right of a participant to refuse participation without

giving reasons must be respected. The participant must remain free to withdraw at any time from the study without giving reasons, and without prejudicing his/her further treatment. The study will be submitted to, and approved by, a main REC and the appropriate Site Specific Assessor for each participating centre prior to entering participants into the study. The CTRU will provide the main REC with a copy of the final protocol, patient information sheets, consent forms, and all other relevant study documentation.

Ethical and Regulatory Approvals for the Conduct of Study

Initial Approval

The trial will be submitted to and approved by a REC, the MHRA, and the Health Research Authority (HRA). The study documents will also be sent to local Research and Development/Innovation departments for each participating site prior to the start of recruitment at site. The CTRU will provide a copy of the final protocol, patient information sheets, consent forms, and all other relevant trial documentation that will be used.

Amendments

Proposed amendments to the protocol and study documents will be submitted for ethical, HRA and, where relevant, regulatory approval by the CTRU, once Sponsor and funder review has been obtained. Amendments requiring approval are to be implemented only after a copy of the approval letter has been obtained.

Urgent safety measures, which result in a substantial trial amendment, may be implemented prior to receiving Sponsor or ethical/regulatory approval. However, approval will be obtained as soon as possible after implementation.

SUSAR Reports, Annual Safety Reports, and End of Trial Notification

The main REC/MHRA will be sent all SUSAR reports and annual safety updates in order to facilitate their continuing review of the study, and will also be informed about the end of the trial, within the required timelines.

Protocol Compliance

Protocol compliance will be assessed throughout the study. Protocol deviations, unplanned non-compliance, or breaches are considered departures from the approved protocol.

Frequently re-occurring deviations are not acceptable and could, potentially, be classified as a serious breach. Prospective, planned deviations or waivers to the protocol are not allowed under the UK regulations on clinical trials.

Protocol violations should be reported immediately to the CTRU using the protocol violations CRF.

Protocol violations that need to be reported include:

- Breaches of the eligibility criteria;
- Drug administration errors related to the study drugs which lead to an SAE (note that other drug administration errors, that do not lead to an SAE, may also constitute a violation)
- Overdose.

If the protocol violation is also associated with an event that meets the criteria of an SAE or SUSAR this should also be reported in accordance with the pharmacovigilance section of the protocol.

16 QUALITY ASSURANCE

16.1 Quality Assurance

The trial will be conducted in accordance with the principles of GCP in clinical trials, as applicable under UK regulations, the NHS RGF (and Scottish Executive Health Department RGF for Health and Social Care 2006 for studies conducted in Scotland), and through adherence to CTRU standard operating procedures (SOPs).

16.2 Serious Breaches of GCP or Trial Protocol

The CTRU and the Sponsor have systems in place to ensure that serious breaches of GCP or the trial protocol are picked up and reported. Investigators will promptly notify the CTRU of a serious breach (as defined in Regulation 29A of the Medicines for Human Use (Clinical Trials) Regulations 2004 [Statutory Instrument 2004/1031], as amended by Statutory Instrument 2006/1928) that they become aware of. A "serious breach" is a breach which is likely to effect to a significant degree:

- (a) the safety or physical or mental integrity of the subjects of the trial; or
- (b) the scientific value of the trial".

Sites should contact the CTRU trial co-ordinators for further information.

16.3 Insurance and Indemnity

Insurance and indemnity for trial participants and trial staff is covered within the NHS Indemnity Arrangements for clinical negligence claims in the NHS, issued under cover of HSG (96)48. There are no special compensation arrangements, but trial participants may have recourse through the NHS complaints procedures.

17 CONFIDENTIALITY

Confidentiality and Data Protection

All information collected during the course of the main trial will be kept strictly confidential. Information will be held securely on paper at the CTRU. In addition, the CTRU will hold electronic information on all trial participants. The CTRU will have access to the entire database for monitoring, co-ordinating, and analysis purposes.

Precautions will be taken to ensure that patient confidentiality is preserved at all times. The patient consent form will identify those individuals who will require access to patient data and identifiable details and obtain appropriate permission from the consenting patient.

The trial staff at participating sites will be responsible for ensuring that any data/documentation sent to the CTRU is appropriately anonymised, as per instructions given by CTRU in accordance with the trial procedures, to conform to the 2018 Data Protection Act.

The CTRU will comply with all aspects of the UK 2018 Data Protection Act. Operationally this will include:

- Explicit written consent from participants to record personal details including name, date of birth, and NHS number;
- Appropriate storage, restricted access, and disposal arrangements for patient's personal and clinical details;
- Consent from participants for access to their medical records by responsible individuals from the research staff, or from regulatory authorities, where it is relevant to trial participation;
- Consent from participants for the data collected for the trial to be used to evaluate safety and develop new research;
- Copies of participants consent forms, which will include patient's names, will be collected when a patient is randomised into the trial by the CTRU. In addition patient name and email address will be collected for questionnaire posting. All other data collection forms that are transferred to, or from, the CTRU will be coded with a unique patient trial number and will include two patient identifiers, usually the patient's initials and date of birth;
- Where central monitoring of source documents by CTRU (or copies of source documents) is required (such as scans or local blood results), the participants name must be redacted by site before sending;
- Where anonymisation of documentation is required, research sites are responsible for ensuring only the instructed identifiers are present before sending to CTRU.

If a patient withdraws consent from further trial treatment and/or further collection of data, their data will remain on file and will be included in the final trial analysis.

18 TRIAL OPERATIONAL STRUCTURE

Chief Investigator

The CI is involved in the design, conduct, co-ordination, and management of the trial. The CI will have overall responsibility for the design and set-up of the trial, the investigational drug supply, and pharmacovigilance within the trial.

Sponsor

The Sponsor is responsible for trial initiation management and financing of the trial as defined by Directive 2001/20/EC. These responsibilities are delegated to the CTRU as detailed in the Delegation of Duties.

Clinical Trials Research Unit

The CTRU at the University of Leeds will have responsibility for the conduct of the trial, in accordance with the NHS RGF and CTRU and Sponsor SOPs, as per the delegation of duties. The CTRU will provide set-up and monitoring of trial conduct to CTRU SOPs, and the GCP conditions and principles as detailed in the UK Medicines for Human Use (Clinical Trials) Regulations 2006 including, randomisation design and service, database development and provision, protocol development, CRF design, trial design, source data verification, monitoring schedule, and statistical analysis and reporting for the trial. In addition the CTRU will support main REC, NHS permissions submissions and clinical set-up, ongoing management including training, monitoring reports, and promotion of the trial. The CTRU will be responsible for the day-to-day running of the trial including trial administration, database administrative functions, data management, safety reporting, and all statistical analyses.

Pharmacy/Grant Holder/Collaborators for Sub Studies

[name] is a co-applicant and a specialist in delivery of the low FODMAP diet and will assume the role of Lead Dietitian. The role of the Lead Dietitian is to provide expertise and training to research sites, either at a face-to-face visit or remotely, in delivery of the low FODMAP diet within the MODULATE trial. Additionally, the Lead Dietitian will be the primary contact for trial dietitians across all sites to provide advice and support for this intervention throughout the duration of the trial. As a co-applicant of the trial, the Lead Dietitian is required to attend TMG meetings to aid decisions in coordination and conduct of the trial. The Lead Dietitian may also be required to participate in analysis and write-up of the study results prior to publication.

19 STATEMENT OF INDEMNITY

Insurance and indemnity for trial patients and trial staff is covered within the NHS Indemnity Arrangements for clinical negligence claims in the NHS, issued under cover of HSG (96)48. There are no special compensation arrangements, but trial patients may have recourse through the NHS complaints procedures.

20 OVERSIGHT/TRIAL MONITORING GROUPS COMMITTEES

Trial Management Group

A TMG will be convened including the CI, co-investigators, and identified key collaborators, the trial statistician, and trial manager. PIs and key study personnel may be invited to join the TMG, as appropriate, to ensure representation from a range of sites and professional groups. Notwithstanding the legal obligations of the Sponsor and CI, the TMG will have operational responsibility for the conduct of the trial.

The TMG terms of reference (ToR) will define the membership, roles, and responsibilities of the TMG, each member of the committee will be required to confirm participation on the committee under the ToR. The TMG will meet monthly. Specifically the TMG will be responsible for: protocol completion, CRF development, obtaining approval from the main REC, HRA and supporting applications for local approvals, submitting a CTA application and obtaining approval from the MHRA, completing cost estimates and project initiation, nominating members and facilitating the TSC and DMEC, monitoring of screening, recruitment, treatment and follow-up procedures, monitoring consent procedures, data collection, and trial end-point validation.

Data Monitoring Ethics Committee

A DMEC will be convened to monitor data collected during the study, and make recommendations to the TSC on whether there are any ethical or safety reasons as to why the trial should not continue. It will consist of an independent chair, an independent statistician, and an independent clinician.

The DMEC ToR will define the membership, roles, and responsibilities of the DMEC. Each member of the DMEC will be required to confirm participation on the committee under the ToR. The DMEC will meet annually as a minimum.

Trial Steering Committee

A TSC will be convened with an independent majority. Participation will include, as a minimum, an independent chair, an independent statistician, an independent clinician, a PPI representative, the CI, the Sponsor's representative, and other members of the TMG as required to update on trial progress. The role of the TSC will be to provide overall supervision of the trial progress and, as necessary, advice to the TMG on operational issues. The TSC will meet annually as a minimum.

The TSC ToR will define the membership, roles, and responsibilities of the TSC. Each member of the TSC will be required to confirm participation on the committee under the ToR.

Public Advisory Group/Patient and Public Involvement (PPI)

The PPI group will be convened to work with the CI to:

- Ensure the trial is carried out in an ethical and respectful way;
- Limit participant burden;
- Maximise recruitment;

- Ensure that the patient perspective is central to decision-making throughout study management;
- Ensure effective, clear communication with participants and the public;
- Anticipate issues that may influence subsequent uptake of any of the interventions should the trial demonstrate effectiveness.

The PPI lead will also be an active member of the TMG, and another patient representative from the advisory group will sit on the TSC. Roles and responsibilities are described in the corresponding ToR.

21 FUNDING

This project is funded by the National Institute for Health Research. (NIHR) Health Technology Assessment (HTA) Programme (Grant Ref: 17/33/03)

22 PUBLICATION POLICY AND DATA DISCLOSURE

The trial will be registered with an authorised registry, according to the International Committee of Medical Journal Editors Guidelines, prior to the start of recruitment.

The success of the trial depends upon the collaboration of all participants. For this reason, credit for the main results will be given to all those who have collaborated in the trial, through authorship and contribution. Authorship decisions will be guided by standard requirements for authorship relating to submission of manuscripts to medical journals. These state that authorship credit should be based only on the following conditions being met (http://www.icmje.org):

- Substantial contribution to conception and design, or acquisition of data, or analysis and interpretation of data;
- Substantial contribution to drafting the article or revising it critically for important intellectual content;
- Substantial contribution to final approval of the version to be published.

In light of this, the CI, other grant co-applicants, and relevant senior CTRU staff will be named as authors in any publications, subject to journal authorship restrictions. In addition, all collaborators will be listed as contributors for the main trial publication, giving details of roles in planning, conducting, and reporting the trial.

To maintain the scientific integrity of the trial, data will not be released prior to the first publication of the analysis of the phase III primary endpoint, either for trial publication or oral presentation purposes, without the permission of the TSC. In addition, individual collaborators

must not publish data concerning their participants that is directly relevant to the questions posed in the trial, until the first publication of the analysis of the primary endpoint.

24 APPENDICES

Appendix 1. Pregnancy Testing

The SPC states that amitriptyline is not recommended in pregnancy, unless clearly necessary, and only after careful consideration of the risk/benefit. NICE guidance recommends the use of TCAs such as amitriptyline for the second-line treatment of IBS, which is at a much lower dose (10 - 30 mg) than it is licenced for in depression (150 mg - 200 mg). In normal practice, patients do not undertake pregnancy testing prior to commencing low dose amitriptyline for treatment of IBS, nor do they undertake pregnancy. Furthermore, amitriptyline has been used for many years in low doses for other conditions, including the treatment of chronic painful conditions, without the need for pregnancy testing.

The MHRA released a Drug Safety Update in January 2020 relating to the use of Ondansetron during the first trimester of pregnancy. This is reflected in the current SPC (26-Nov-2019) and warns against the use of Ondansetron in the first 12 weeks of pregnancy due to the slight increased risk of orofacial malformations based on human experience in epidemiological studies.

Pregnancy is an exclusion criteria in this study: any woman who is pregnant, or is planning to become pregnant during the time period covered by the trial, will be refused entry into the trial. All women of childbearing potential (defined as women who have had any menstrual bleeding

in the last 12 months and who are not surgically sterile) must undertake a pregnancy test prior to study entry and be willing to use medically approved contraception whilst receiving treatment.

Appendix 2. Shipment of Study Medication Directly to Patients Via Royal Mail Signed For® 1st Class Delivery

Delivery of the study medication by Royal Mail Signed For® delivery directly to participant's home address under ambient shipping conditions, has been risk assessed and considered acceptable and appropriate based on the following:

- None of the IMPs used in this study are controlled drugs;
- Amitriptyline is widely prescribed in primary care with over 50 years of use data. It is being used at a low dose (10mg rather than 75mg tablets).
- Ondansetron has been widely used for nearly three decades and at the doses used in this study has shown to be extremely safe.
- Loperamide is available over the counter to buy and known to be extremely safe.
- All three drugs are stable with a good margin of safety and a long shelf life. Study medication will be re-packaged to ensure it is protected from light and moisture.
- The IMPs will be dispensed by the site pharmacy as per local practice and posted to the patient under ambient shipping conditions. This is similar to clinical practice and standard care where a patient would take the medication home with them in ambient conditions once it has been dispensed.
- Recorded delivery must be used to ensure the intended recipient receives the medication and to prevent an unintended person picking up study medication that has been posted through the door. Participants will confirm receipt of the medication. In the event that they do not receive the medication, central pharmacy will keep a log of the tracking numbers so that the parcel can be traced.
- Low dose (10mg) amitriptyline is being sent, using small quantities while at the same time keeping the study logistically possible. Therefore in the unlikely event that the medication is received by an unintended recipient, the amount they have access to has been limited.

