5.1 Inclusion Criteria

- 1. A histological diagnosis of UC in secondary care, including left-sided colitis or extensive colitis.
- 2. Age ≥18 years.
- 3. At least moderate discomfort from diarrhoea according to the GSRS-IBS [26] (equating to a score of ≥4 on the diarrhoea subscale of the GSRS-IBS)
- 4. On stable doses of UC-related medication for ≥2 months at time of initial screening telephone call.
- 5. Ongoing diarrhoea for 3 months prior to initial screening telephone call.
- 6. A CRP <5mg/L (measured as per local practise) within 4 weeks prior to randomisation.
- 7. FC <250mcg/g [29] within 4 weeks prior to randomisation.
- 8. Stable UC at the time of randomisation, in the clinical opinion of the gastroenterologist¹,
- 9. No evidence of active suicidal ideation at time of initial screening telephone call and prior to randomisation, as determined by the three clinical screening questions below²:
 - a. Whether the patient has experienced any thoughts of harming themselves, or ending their life in the last 7-10 days?
 - b. Whether the patient currently has any thoughts of harming themselves or ending their life?
 - c. Whether the patient has any active plans or ideas about harming themselves, or taking their life, in the near future?
- 10. No recent history of self-reported self-harm (an episode of self-harm within the last 12 months).
- 11. Willing to be considered for all treatment arms of the trial, and to remain in the treatment arm to which they are assigned.
- 12. If female must be:
 - a. post-menopausal (no menses for 12 months without an alternative medical cause), or;
 - b. surgically sterile (hysterectomy, bilateral salpingectomy or bilateral oophorectomy), or;
 - ^{c.} using highly effective contraception (and must agree to continue for 7 days after the last dose of the investigational medicinal product [IMP]). ³
- 13. Able to complete questionnaires and trial assessments.
- 14. Able to provide written informed consent.

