5.2 Exclusion Criteria

- 1. Inflammatory bowel disease unclassifiable or Crohn's disease.
- 2. Ulcerative proctitis.
- 3. Body mass index≤18.5 kg/m².
- 4. Previous or planned gastrointestinal IBD-related resectional surgery or previous cholecystectomy.

- 5. Having received steroids for UC within the last 2 months prior to the initial screening telephone call or at randomisation.
- 6. Coeliac disease (as confirmed via anti-tissue transglutaminase (tTG) antibodies).
- 7. A previous diagnosis of colorectal dysplasia or cancer, or no up to date surveillance colonoscopy, as per current British Society of Gastroenterology guidelines [30].
- 8. Known allergy to TCAs, ondansetron, or loperamide.
- 9. Current use of a TCA at the time of the initial screening telephone call or at randomisation.
- 10. Previous failed treatment with, or regular use of amitriptyline, ondansetron, or loperamide for diarrhoea.
- 11. Currently on, or have previously tried and failed, a low FODMAP diet under dietitian guidance.⁴
- 12. Contraindications⁵ to the current use of TCAs including patients with any of the following:
 - a. taking monoamine oxidase inhibitors, or receiving them within the last 2 weeks;
 - b. already currently prescribed a TCA for the treatment of depression
 - c. previous myocardial infarction;
 - d. recorded arrhythmias, particularly heart block of any degree, or prolonged Q-T interval on electrocardiogram;
 - e. mania;
 - f. severe liver disease;
 - g. porphyria;
 - h. congestive heart failure;
 - i. coronary artery insufficiency;
 - j. receiving concomitant drugs that prolong the QT interval (e.g. amiodarone, terfenadine, or sotalol).
- 13. Contraindications to the current use of ondansetron, including:
 - a. concomitant use of apomorphine;
 - b. concomitant use of other drugs that prolong the QT interval.
- 14. Contraindications to the current use of loperamide, including:
 - a. acute UC;
 - b. acute dysentery, which is characterised by blood in stools and high fever;
 - c. bacterial enterocolitis caused by invasive organisms;
 - d. pseudomembranous colitis associated with the use of broad-spectrum antibiotics.
- 15. Pregnancy, planned pregnancy during the study, pregnancy within 3 months of study completion, or breastfeeding⁶.

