²Suicidal ideation should be assessed on the screening telephone call. No more than 14 days should elapse between the initial suicidal ideation assessment and study entry/ randomisation. If more than 14 days have elapsed then the suicidal ideation assessment should be repeated. ³Highly effective contraception is defined as one of the following: combined (oestrogen and progestogen-containing) hormonal contraception associated with inhibition of ovulation (oral, intravaginal, or transdermal); progestogen-only hormonal contraception associated with

¹ A flexible sigmoidoscopy with Mayo score ≤1 is only required if there is clinical uncertainty regarding the stability of the patient's UC and is at the discretion of the treating physician. Rectal bleeding reported by the patient would contribute to the assessment of disease stability and if present should be assessed by flexible sigmoidoscopy.

inhibition of ovulation (oral, injectable, or implantable); intrauterine device (IUD); intrauterine hormone-releasing system (IUS); bilateral tubal occlusion; vasectomised partner; practising true abstinence (defined as refraining from heterosexual intercourse, when this is in line with the preferred and usual lifestyle of the subject).

⁴Patients currently waiting to see a dietitian for a low FODMAP diet must agree not to commence seeing a dietitian unless they are randomised to the low FODMAP arm of the trial. ⁵Cautions to the use of TCAs will not be an exclusion, but these will be recorded at screening and clarified with the patient's gastroenterologist and the principal investigator (PI) in each centre prior to study entry. These include cardiovascular disease; diabetes; epilepsy; history of psychosis or bipolar disorder; hyperthyroidism; increased intra-ocular pressure; phaeochromocytoma; prostatic hypertrophy (prostate gland enlargement); susceptibility to angle-closure glaucoma; difficulty passing urine.

⁶ For women of childbearing potential (those not post-menopausal or surgically sterile) a pregnancy test must be performed within 7 days prior to randomisation. Post-menopausal is defined as no menses for 12 months without an alternative medical cause.

6. Recruitment Process

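### Appendix 1 defines childbearing potential more narrowly than sections 5 and 6.8, so a woman with 12 months' amenorrhoea from another medical cause must be pregnancy-tested under the main text but falls outside the appendix

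*Protocol*

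**What the plan says.** Three places in the main text agree on who needs a test. Footnote 6 to section 5.2 reads: "For women of childbearing potential (those not post-menopausal or surgically sterile) a pregnancy test must be performed within 7 days prior to randomisation". It then says: "Post-menopausal is defined as no menses for 12 months without an alternative medical cause". Inclusion criterion 12 in section 5.1 carries the same qualifier for post-menopausal status and lists what counts as "surgically sterile (hysterectomy, bilateral salpingectomy or bilateral oophorectomy". Section 6.8 (Screening Assessments) repeats the footnote 6 definition and the 7-day window.

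On contraception, a woman who is neither post-menopausal nor surgically sterile satisfies criterion 12 only by "using highly effective contraception (and must agree to continue for 7 days after the last dose of the investigational medicinal product [IMP"]). Footnote 3 gives a closed list of methods that qualify.

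Appendix 1 (Pregnancy Testing) words all of this differently. It opens with "All women of childbearing potential (defined as women who have had any menstrual bleeding" and continues "in the last 12 months and who are not surgically sterile) must undertake a pregnancy test prior to study entry". The same sentence asks these women to "be willing to use medically approved contraception whilst receiving treatment".

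The pregnancy row of the safety monitoring plan (section 12, Table 2) says that women of childbearing potential will be tested before entry, gives no definition of its own, and points to Appendix 1 for further information.

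**The concern.** A protocol should classify a given woman in one way. Here the year without periods is qualified in section 5 and unqualified in Appendix 1, and this changes whether a pregnancy test is required. Appendix 1 is written as an obligation, carries the title Pregnancy Testing, and is where the safety monitoring plan sends the reader.

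Eligibility is confirmed before allocation is known, so every woman entering the trial may be allocated to a drug arm. The protocol attaches a pregnancy warning to each drug: a slightly raised risk of orofacial malformation with first-trimester ondansetron (Appendix 1), and statements in section 12 that pregnancy is not recommended with amitriptyline or ondansetron and not advisable with loperamide. In addition, section 5 permits no eligibility waivers, and section 15 makes breaches of the eligibility criteria reportable protocol violations. A site acting in good faith on the appendix could therefore commit such a violation.

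**Working it through.** No sample size, power or error-rate figure is involved. The check is to classify each kind of woman under the two definitions.

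| Woman | Sections 5 and 6.8 | Appendix 1 |
|---|---|---|
| (a) Bled within 12 months, no sterilising surgery | Test | Test |
| (b) No bleeding for 12 months, no other cause | No test | No test |
| (c) Hysterectomy, bilateral salpingectomy or bilateral oophorectomy | No test | No test |
| (d) No bleeding for 12 months, another medical cause, not surgically sterile | Test | Outside the definition |
| (e) Bilateral tubal occlusion, still bleeding | Test (footnote 3 lists it as contraception; criterion 12 does not list it as sterility) | Unclear (surgical sterility is not defined there) |

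Rows (a) to (c) agree. Row (d) is a definite conflict: the footnote 6 qualifier keeps this woman out of the post-menopausal group, while the bleeding-only rule removes her from the Appendix 1 group. Row (e) is an ambiguity.

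The mismatch runs in one direction. The main text catches women whom the appendix leaves out, and no row shows the reverse.

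Row (d) has a second consequence. If such a woman uses no contraception, she meets none of the three routes in criterion 12 and is ineligible. The Appendix 1 sentence on testing and contraception does not apply to her at all.

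Two further differences:

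- **Test timing.** Footnote 6 and section 6.8 set a 7-day window before randomisation. Appendix 1 says only that the test precedes study entry.
- **Contraception.** Section 5 requires a method from a closed list, continued until 7 days after the last dose. Appendix 1 gives a general standard with no list and stops at the end of treatment.

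For scale, section 13.1.1 allocates 66 of 396 phase 2 participants to each active arm. The three drug arms hold 3 × 66 = 198, and 198/396 = 50%. The ondansetron arm holds 66/396, or one sixth. These are shares of all participants. The protocol gives no figure from which to estimate how many are women in row (d).

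**The case against.** The best defence is that the operative text is consistent. Section 5 decides eligibility, section 6.8 is the screening instruction that sites carry out and it repeats the section 5 definition, and footnote 5 to the screening table in Appendix 5 keeps the 7-day rule with a home test as back-up. A medically trained doctor must confirm eligibility before randomisation. Most of Appendix 1 is background on why testing exceeds usual care, and section 12 offers it as further information, not as the rule to apply. All of this stands, and it keeps the practical effect modest. It does not remove the conflict, because the Appendix 1 sentence is worded as a requirement and the pointer to it exists.

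Four stronger readings are tempting, and the documents do not support them:

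- **That the contraception rules cannot both be met.** A woman who satisfies criterion 12 through contraception also satisfies the looser Appendix 1 sentence, and that sentence does not waive criterion 12. The fault is inconsistent wording for one requirement.
- **That exclusion 15 adds a third contraception period.** "Pregnancy, planned pregnancy during the study, pregnancy within 3 months of study completion, or breastfeeding" concerns pregnancy, not how long contraception continues after the last dose. The two rules have different objects and can both be met.
- **That all the study drugs are teratogenic.** The protocol states a malformation risk, described as slight, only for ondansetron in the first 12 weeks. For amitriptyline and loperamide it gives general cautions.
- **That women without periods because of a listed hormonal contraceptive show the harm most clearly.** They already use a method that criterion 12 accepts. Amenorrhoea from another medical cause is the clearer case.

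**Conclusion.** The point holds in a limited form. Appendix 1 and sections 5 and 6.8 classify one group differently: non-sterile women with at least 12 months' amenorrhoea from another medical cause. Appendix 1 is also looser on test timing and contraception. This deserves correction as a participant-safety eligibility rule, although the effect in practice should be modest.

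A reader might infer that untested women will be randomised. The documents do not support that, since a site following section 5 or section 6.8 would test them. The breach arises only if a site relies on Appendix 1 instead. The conclusion rests on reading the appendix definition literally and on section 5 governing eligibility. The number of women affected cannot be derived, and no endpoint, power or error rate is touched.

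**What to change.** Reconcile criterion 12, footnote 6, section 6.8, the pregnancy row of the safety monitoring plan in section 12, and Appendix 1, so that one definition of childbearing potential, one test window and one contraception requirement apply throughout. What each should say is for the sponsor's clinical and regulatory leads. This review does not prefer either wording, and simply deleting the Appendix 1 sentence would itself choose between them. When the text is aligned, surgical sterility should carry the same meaning wherever it is used.

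The cost is a text amendment with its usual approvals. The pregnancy test is already in the schedule of events, so removing the inconsistency does not in itself require a new procedure.
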